Appendix F for detailed Monitoring Plan for Monoclonal Expansion and Insertional Oncogenesis)

6. Measurements of erythrocyte ADA enzymatic activity and deoxyadenosine metabolites in RBC

Immune function testing:

7. Determination of absolute numbers of CD3+, CD4+ and CD8+ T lymphocytes, CD19+ B lymphocytes and CD56/CD16+ NK cells, and CD4+/CD45RA+ and CD4+/CD45RO+
8. Proliferative responses to PHA, tetanus toxoid at baseline, 6, 12, 18, and 24 months and to tetanus toxoid only after immunization to tetanus
9. Measurement of serum immunoglobulin levels (IgG, IgA, IgM)
10. Specific antibodies to tetanus toxoid, polyribosylphosphate (PRP, Q 3 months if not receiving IVIg)
11. TCR V β panel, TREC

Gene transduction/expression:

12. Measurement of the frequency of cells containing the inserted ADA gene in PBMC and granulocytes as well as FACS-sorted T cells and myeloid cells by PCR
13. Measurement of ADA expression in leukocytes and erythrocytes by ADA enzymatic assay

Blood samples to be obtained at each^{1,2} post-infusion time point.

Test	Tube Type	Minimum Vol.	Destination
Serum metabolic panel, including Electrolytes	Red Top Tube	2.0 ml	Clinical Lab
CBC, differential	Purple Top Tube	1.0 ml	Clinical Lab
Erythrocyte ADA activity and dAXP	Green Top Tube (ice)	2.0 ml	Duke/[name]
PBMC for Lymphocyte Immunophenotype and Proliferation and TCR V β Usage ³	Purple Top Tube Green Top Tube	2 X 2.0 ml 4.0 ml	Clinical Immunology Lab and Gene Therapy Core
PBMC for ADA enzyme assay (optional, for research)	Green Top Tube Purple Top Tube	8.0 ml 5 ml	Gene Therapy Core

PBMC for vector (ddPCR/qPCR and VISA), TREC			
PBMC for RCL ¹			
Serum for WB for RCL ²	Tiger Top Tube	2.0 ml	Gene Therapy Core
Serum for Ig levels	Tiger Top Tube	2.0 ml	Clinical Lab

¹ PBMC for RCL will be done at baseline, 3, 6, 12 & 24 months, then archived annually thereafter

² Serum (for Western Blot [WB]) will be archived at baseline, 3, 6, 12 and 24 months, then annually thereafter

³ Flow cytometry, NIH

Other research tests

These tests will be performed, only as appropriate, to address outcome(s) and mechanism(s) of action of the treatment. For example, we may look at T cell receptor (TCR) spectratyping from PBMCs and/or serum cytokine levels. No extra blood will be drawn for these tests; tests will be performed on existing or left-over samples from the follow-up periods defined above.

Hierarchy of tests if samples are limited:

Due to the large number of blood tests planned and the limited volumes of blood that may be obtained from young children, it may not be possible to perform every scheduled investigation at each time-point. Therefore, the hierarchy for priority of blood tests will be:

1. Safety studies: CBC w/diff, platelet count, chemistry panel & electrolytes, LAM-PCR (see [Schmidt et al 2001](#), for description of method)
2. Monitoring ADA levels: leukocyte and erythrocyte ADA enzyme levels and RBC dAXP levels
3. Immunologic function studies
4. Gene marking/expression
5. Other research tests

B. Diagnostic bone marrow aspirates:

Bone marrow aspirates may be requested at 1 or 2 time-points in the first two years after treatment. Bone marrow samples will be used to evaluate the presence of cells containing the vector sequences by DNA-PCR of BM cells. These aspirates will be performed under conscious sedation, and parents are free to refuse these post-treatment marrow aspirates, as stated in the initial informed consent document.

C. Immunizations:

When patients have evidence of adequate immune reconstitution (absolute CD4+ $\geq 100/\text{mm}^3$) at least one year after transplantation, immunization will be given with DT (or DPT, DTaP, or Tdap) and IPV every two months, for a total of three dosages. For children who have IVIg administration

stopped, vaccination will follow guidelines for post-allogeneic HSCT vaccinations as in [Griffith et al, JACI 2009](#). If they are below normal, re-immunization with DT will be given. Annual seasonal influenza vaccination (not attenuated nasal) is recommended for subject and family.

D. Extended follow-up:

The current study plans call for follow-up for a total of two years. However, the subjects will be followed clinically beyond this point, as would any subject with an immunodeficiency disease. Standard care would also involve evaluation of immune function at least quarterly by measuring lymphocyte numbers and function (PHA, tetanus toxoid blastogenesis). Gene marking will also be evaluated as outlined in the monitoring plan, unless no gene-containing cells are seen on successive studies over twelve months. Peripheral blood serum and PBMC will be stored annually, in case assays for RCL exposure are needed. Effort will be made to continue these studies as long as possible, although it is not possible to promise life-long follow-up. The plans for life-long follow-up for the detection of RCL and the 15-year follow-up for leukemia monitoring are described in [Appendix F](#). In the case of the death of the subjects, autopsies will be requested from appropriate next-of-kin. Tissues will be analyzed for the presence of gene-containing cells and for the presence of RCL.

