4.2 Study Endpoints

4.2.1 Primary Endpoints

4.2.1.1 Evaluation of Safety

Primary Endpoint: Incidence and grade of Serious Adverse Events (SAE).

Serious adverse events may be manifest as:

- a) clinical toxicities
- b) exposure to replication-competent lentivirus (RCL)
- c) development of monoclonal expansion or leukoproliferative complications from vector insertional effects.

a) To detect potential clinical toxicities from the treatment, patients will have interval medical histories taken, complete physical examinations, and phlebotomy to obtain peripheral blood for laboratory studies on day +1, and then at months 1, 2, 3, 4, 5, 6, 8, 10, 12, 15, 18, 21 and 24 (+/- 4 weeks). Laboratory studies performed at these time-points will include CBC with differential and platelet count and a chemistry panel and electrolytes. Toxicities relative to the clinical parameters, the CBC with differential, and the chemistry panel are defined by an adapted Pediatric Clinical Toxicity Scale from the NIAID, Division of AIDS. ([Appendix G](#))

Patients will also be monitored by clinical examination and laboratory studies in the immediate period (3 to up to 6 weeks, depending on clinical course) after infusion of OTL-101 to monitor myelosuppression expected from the administered busulfan.

b) To detect exposure to replication-competent lentivirus:

i. PBMC will be assayed by PCR to detect RCL. This test will be performed by the National Gene Vector Biorepository on samples obtained at baseline (pre-infusion), 3, 6, 12 and 24 months post-infusion. Samples will also be collected annually thereafter, and cells archived for PCR assay, to be run if any samples are positive.

ii. Serum for measurement of antibody to RCL will be archived for the presence of antibody to VSV-G envelope at baseline (pre-infusion), 3, 6, 12 and 24 months post-infusion (and annually thereafter).

c) To monitor for monoclonal expansion or leukoproliferative complications, LAM-PCR will be performed, as described in [Appendix F](#).

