If by 6 months after cell product infusion, there is no evidence of PBMC or erythrocyte ADA enzyme activity (over baseline/pre-treatment levels), immune reconstitution ($<200/\mu\text{L}$ absolute CD3+ T) and no detectable ADA gene-marking in granulocytes by ddPCR/qPCR ($<1/100,000$), PEG-ADA will be re-started.

Patients will be monitored for clonal expansion, once gene marking levels exceed 1% (see detailed monitoring schedule in [Appendix F](#)).

Long-term follow-up: After completion of the two years of post-treatment evaluation of this study, patients will be offered enrollment in a long-term follow-up study. We will attempt to maintain annual contact with all treated subjects and will obtain samples of peripheral blood cells and serum annually for archiving at -80°C , to be available for investigation of potential complications related to lentiviral-mediated gene transfer, e.g. to assess the presence of serum antibodies to lentiviral vector proteins, the presence of replication-competent lentivirus in peripheral blood cells or clonal dominance.

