9.9 Halting Rules for the Protocol

If any one of the following five instances occurs, new enrollment to the protocol or treatment of subjects will be halted, pending investigation of the cause. Findings will be discussed with the FDA, IRB and DSMB and each must agree to conditions by which the study can be resumed before enrolling the next patient. Evaluations of study endpoints of subjects already enrolled and who received the final cell product will continue to be performed.

1. If there is one death or four grade 4 toxicities (except grade IV busulfan-related hematologic serious adverse events {transient leukopenia, anemia, thrombocytopenia resolving within 42 days of transplant} which are anticipated and will be reported, but will not be considered stopping

criteria). Additionally, neutropenia (a documented disorder of ADA-deficiency) occurring at any time, will be graded for severity but will not count towards the stopping rule.

2. If two subjects have prolonged unresponsive pancytopenia. This is defined as initial failure at hematologic reconstitution which does not improve following administration of the back-up marrow. Failure of hematologic reconstitution is defined as at least any two of the following being: ANC $<200/\text{mm}^3$, and/or platelets $< 20,000/\text{mm}^3$ without transfusions, and/or Hb $< 8.0 \text{ gm/dl}$ without transfusions) on three independent and consecutive determinations over at least ten days beyond day +42 from initial infusion of the cell product. If these conditions are reached, the back-up marrow will be infused IV. If failure of hematologic reconstitution persist after the back-up marrow has been given through day +90 from the initial infusion of the cell product, prolonged unresponsive pancytopenia will exist.

3. If 0 of 3 successive patients show evidence of engraftment of transduced cells by six months of follow-up (all peripheral blood samples negative by ddPCR/qPCR for vector sequences ($<1/10,000$) or by ADA enzyme assay).

4. If RCL is detected, and confirmed in one subject.

5. If a subject in this study develops hematological proliferative, monoclonal expansion or malignant disease (excluding DFSP). A thorough investigation of the cause of the proliferation, expansion or malignancy, including proviral integration analysis, will be done.

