Insertional oncogenesis following gene transfer into hematopoietic stem cells could theoretically result in either lymphoid or myeloid leukemias. The techniques used to characterize the T cell lymphoproliferation occurring in X-SCID patients after gene therapy may not be adequate for other forms of malignant expansion, and it is important that monitoring protocols are identified that can be applied to all patients and possible different outcomes.

MONITORING PROPOSAL: GENE TRANSFER TO CD34+ HEMATOPOIETIC STEM CELLS

¹ A approximately every 6 months for the first 5 years on study, then annually for the next 10 years. (If at 2 years, marking is low or absent, and / or monoclonality is stable, the plan may be modified with regulatory agency guidance). CBC = complete blood count with differential; LAM-PCR = ligation/amplification mediated polymerase chain reaction; PBMC = peripheral blood mononuclear cells; S.D. = standard deviation; TCR = T cell receptor; EBV = Epstein-Barr virus; BCR = B lymphocyte receptor; BM = bone marrow.

Protocol for monitoring and evaluation of increasing oligoclonality or monoclonality:

In order to monitor subjects for evidence of uncontrolled leukocyte proliferation, the following protocol will be used:

1. Clinical Assessment

Clinical evaluation for evidence of leukocyte proliferation, or cytopenia - Physical evaluation and imaging studies (as indicated) for evidence of lymphadenopathy, hepatomegaly, splenomegaly.

2. Screening Laboratory Assessment

CBC with differential to determine whether there is evidence of leukocytosis, or cytopenia. Leukocytosis will be defined as values that are $> 15,000 / \text{mm}^3$ on two successive analyses, within a clinically-appropriate time-frame and in the absence of signs of infection. Cytopenia will be defined as platelets $< 100,000/\text{ul}$, leukocytes $< 1,500/\text{ul}$, or hemoglobin $< 10 \text{ g/dl}$.

[Routine follow-up will also include serum electrolytes, creatinine, BUN, LDH, uric acid, AST, ALT, alkaline phosphatase].

Quantitative PCR for the frequency of gene-modified peripheral blood mononuclear cells (PBMC). LAM-PCR, if frequency of gene-modified PBMC $> 1\%$.

If the LAM-PCR results suggest monoclonality, then the following laboratory assessments will be performed, as applicable:

3. Detailed Laboratory Assessment

To determine which cell population may contain an abnormally proliferating clone, immunophenotyping¹ and FACS sorting² will be performed on peripheral blood:

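### When blood is short, the Appendix B order of tests gives RCL testing no rank and puts the vector PCR that triggers LAM-PCR at level four

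*Protocol*

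**What the plan says.** Protocol Appendix B, III.A sets a priority order for small samples. Its reason is "Due to the large number of blood tests planned and the limited volumes of blood that may be obtained from young children", and it warns that "it may not be possible to perform every scheduled investigation at each time-point". The five levels are:

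1. "Safety studies: CBC w/diff, platelet count, chemistry panel & electrolytes, LAM-PCR"
2. "Monitoring ADA levels: leukocyte and erythrocyte ADA enzyme levels and RBC dAXP levels"
3. Immune function studies
4. Gene marking and expression
5. Other research tests

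Elsewhere the protocol gives RCL and vector PCR safety roles:

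- Section 4.2.1.1 names RCL exposure as component (b) of the primary safety endpoint and says "PBMC will be assayed by PCR to detect RCL". Appendix B schedules this at baseline and at 3, 6, 12 and 24 months, and lists it with the safety and toxicity studies.
- Section 9.9, halting rule 4, reads "If RCL is detected, and confirmed in one subject".
- Section 7.5 says "Patients will be monitored for clonal expansion, once gene marking levels exceed 1" per cent. Appendix F, under screening laboratory assessment, says "LAM-PCR, if frequency of gene-modified PBMC" is above 1%. Section 7.6.1, item 12, repeats that LAM-PCR for leukaemia monitoring is run only when its trigger is met.

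SAP 8.4.3 will give the number and percentage of treated subjects positive for RCL, by visit and at any time. It does not say how untested children enter the denominator.

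**The concern.** A priority list matters only when something has to be dropped. A site that follows this one has no instruction to keep blood for RCL PCR. It is also told to complete ADA levels and all immune function tests before vector PCR. Yet the vector PCR result decides whether LAM-PCR, a level-one test, is done at all.

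Two things are at stake at a short visit. The first is RCL detection. After infusion the patient PCR is the only routine RCL test: the archived cell product is assayed only if a patient sample is positive (Section 6.1, certificate of analysis), the RCL serum is only banked, and later annual samples are run only after a positive (Section 4.2.1.1). The second is the gate to clonal monitoring, which feeds halting rule 5. There is also a reporting risk: no positives among those tested could be read as no positives among all 20 treated.

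**Working it through.** There is no plan figure to reproduce. The check sets the hierarchy against the rules that use each test, then adds up the volumes.

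**Where each test ranks and what uses it**

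| Test | Rank when blood is short | Used by |
|---|---|---|
| CBC, chemistry | 1 | Safety monitoring |
| LAM-PCR | 1, but only if marking exceeds 1% | Clonal monitoring, halting rule 5 |
| ADA enzyme, dAXP | 2 | Halting rule 3 (the enzyme assay is one route) |
| Vector PCR | 4 | LAM-PCR trigger, halting rule 3 (other route) |
| RCL PCR | none | Primary safety component (b), halting rule 4 |

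**Volumes.** These are the minimum volumes in the Appendix B tube table, which is broken in the extracted text. I read the 5 mL tube as the vector PCR tube and leave out the 8 mL tube marked optional for research.

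- Level 1, chemistry and CBC: 2 + 1 = 3 mL
- Level 2, erythrocyte ADA and dAXP: 3 + 2 = 5 mL
- Level 3, immunophenotype, proliferation and immunoglobulins: 5 + (2 × 2) + 4 + 2 = 15 mL
- Level 4, vector PCR tube: 15 + 5 = 20 mL
- Banked RCL serum where due: 20 + 2 = 22 mL

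Section 7.6.1 lists 2 mL each for LAM-PCR and RCL PCR. If LAM-PCR is a separate draw, vector PCR starts after 15 + 2 = 17 mL and is complete at 22 mL. With separate RCL PCR and RCL serum as well, the visit needs 22 + 2 + 2 = 26 mL.

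**When would the order bind?** The documents give no draw limit and no weights. Assume 5 kg and 1 to 5 mL/kg per visit, that is 5 to 25 mL. At 1 to 3 mL/kg (5 to 15 mL) vector PCR is not reached. At 5 mL/kg (25 mL) it is. The draw needed to complete level 4 falls with weight: 20/5 = 4.0 mL/kg at 5 kg and 20/10 = 2.0 mL/kg at 10 kg.

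**What would level 1 need if repaired?** CBC and chemistry 3 + LAM-PCR 2 + RCL PCR 2 + vector tube 5 = 12 mL, or 12/5 = 2.4 mL/kg at 5 kg. RCL PCR accounts for only 2 mL of this.

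**RCL follow-up.** There are 4 post-infusion PCR time points per child, so 4 × 20 = 80 in the trial. One missed sample is a quarter of that child's RCL follow-up in the study.

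**The case against.** The strongest reply is that level one already protects the specimen. In the Appendix B schedule, LAM-PCR is a footnote to the vector PBMC row at 6, 12, 18 and 24 months, and the tube table may show vector, integration-site and RCL samples in one block. On that reading, keeping the LAM-PCR sample also secures material for vector PCR at those visits, and for RCL PCR at 6, 12 and 24 months, leaving only month 3 exposed. This is possible, but the table is broken, Section 7.6.1 lists separate specimens, and the hierarchy does not say it. If the tube is instead dropped as a level-four item, a shared tube loses both tests. RCL could also be read into the words for safety studies, but the itemised list leaves it out.

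Other replies stand and limit the point:

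- Vector PCR is scheduled at 13 post-infusion visits, so one missed value delays the 1% trigger and does not disable it. Section 7.6.1, item 13, also plans integration-site analysis without the 1% condition.
- The vector lots are screened for RCL before use, unused PBMC are frozen at each visit, and the visit window is four weeks either way.
- Enrolment had closed by October 2016 with 20 treated (Section 2.1.6.2). The last protocol version listed is dated 28 March 2018, 17 months later. By then, of the in-study RCL draws, only month 24 could still lie ahead.

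A reader might infer that small infants lose the primary safety monitoring, or that halting rules 3 and 4 are disabled together. The documents do not support either. The primary safety endpoint is the incidence and grade of SAEs; history and examination need no blood, and CBC and chemistry come first. Halting rule 3 can also be read from the ADA enzyme assay at level two. The LAM-PCR trigger does not use RCL. Nor can it be said that the limit binds often, or at 28 to 30 mL per visit: that total includes the optional 8 mL tube, and no draw limit is stated.

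**Conclusion.** The conflict is in the text and should be corrected. The hierarchy gives RCL testing no place, against Section 4.2.1.1, the Appendix B safety list and halting rule 4. It also makes a level-one test depend on a level-four result. What can be lost at a short visit is RCL detection and the gate to clonal monitoring at that visit, and no more than that.

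The size is uncertain. A visit needs about 20 to 22 mL by the table's minimum volumes, with vector PCR reached after about 15 to 17 mL. These figures assume that the 5 mL tube is the vector tube and that the optional tube is left out. How many visits were affected cannot be told from the documents. Because enrolment is closed, reordering the tests can help only the remaining visits; the denominator in SAP 8.4.3 matters for every visit already done.

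**What to change.** Reconcile the Appendix B safety list, the Appendix B hierarchy, Section 9.9 and Appendix F. In the hierarchy, name within level one RCL PCR at its scheduled visits and the PBMC vector PCR that gates LAM-PCR, for the remaining visits. Granulocyte marking need not move up, and no redraw rule is needed. State in the tube table whether the vector, LAM-PCR and RCL samples share a tube.

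In SAP 8.4.3, report the number tested for RCL at each visit, use it as the denominator for that visit, and show how many of the 20 treated children were not tested.

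The cost is one short protocol amendment and one extra row in an SAP table, with no new test. The real price is that at low-volume visits some ADA-metabolite or immune-function values may be lost instead. Those values are also used in patient care, so the investigators should accept that trade explicitly.

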17.3 Appendix C: EFS-ADA Trial Busulfan Pharmacokinetic Analysis

Purpose: Subjects will receive one dose of busulfan, @ 4 mg/kg. Busulfan blood levels will be measured following the busulfan to calculate the area-under the curve (AUC). Because only a single dose of busulfan is given, no dose adjustment will be made.

Method: Busulfan dose is Busulfex 4 mg/kg IV x 1 dose. Blood samples are taken at specified times after the dose of busulfan is infused. The busulfan levels in each sample will be measured in the laboratory and the projected net AUC calculated.

[figure not shown]
Sampling: Busulfan is administered IV over 3 hours. As soon as busulfan infusion is complete, flush CVC with 5cc NS before drawing first level. Draw first level immediately, to measure end-of-infusion peak (t=0 min). Then, draw other samples, timed from the end of the busulfan infusion: 1, 2, 4, 8, and 13 hours after the end of busulfan infusion.

Sample Times (min.)

1)	0	(immediately at end of 3 hr infusion)
2)	60	(1 hr)
3)	120	(2 hr)
4)	240	(4 hr)
5)	480	(8 hr)
6)	780	(13 hr)

The whole blood samples are processed by centrifugation and plasma fractions are frozen at -20°C until the complete set of samples for the dose are obtained.

Calculation: Plasma busulfan levels are determined by HPLC. Busulfan pharmacokinetic parameters are calculated by fitting a bi-exponential equation. Area-under-the curve (AUC) is calculated by trapezoidal approximation, while drug clearance (optional) is calculated by using the busulfan dose divided by both body weight and the measured AUC.

ANNUAL REVIEW

PRINCIPAL INVESTIGATOR	DATE

Purpose:

To ensure that hematopoietic progenitor cell products are transported in such a way as to protect the integrity of the product and the health and safety of personnel transporting the product.

Principles: Not Applicable.

Definitions:

Excipient: An inert substance used as a diluent or vehicle for a drug.

Materials:

Room temperature (20 - 25°C) gel ice pack (approx. 900 grams).

Shipping container (MiniMate Ice Chest #1 or #2) labeled “Hematopoietic Progenitor Cells” and with permanent shipping label inside and outside of container. See label example at end of procedure.

Wet ice (if applicable).

Dry ice (if applicable).

Ziplock®-type plastic bags (9” x 12”), pre-sterilized.

Liquid Nitrogen and LN₂ Shipper.

Specimen Requirements:

Whole blood, bone marrow, or Hematopoietic Progenitor Cells in excipient.

Safety Precautions:

Universal precautions are used. All patient specimens are treated as if infected by blood-borne pathogens, and therefore, gloves must be worn when handling specimens.

References:

Foundation for the Accreditation of Hematopoietic Cell Therapy (FACT) Accreditation Manual, Section D, 2nd Edition, 2002.

“Circular of Information for the Use of Cellular Therapy Products”, American Association of Blood Banks, America’s Blood Centers, American Red Cross, ASBMT, FACT, NMDP, ISCT, 2003.

Procedure:

Before a cell product is collected and transported, the following orders must be issued:

An order to collect the cell product.

An order to receive the cell product in the Bone Marrow (BM)/Hematopoietic Stem Cell (HPSC) Lab.

An order to release the cell product from the BM/HPSC lab to the Clinical Gene Therapy Laboratory (CGTL).

Cell Products:

Hematopoietic Progenitor Cells, Apheresis (HPC, A) is collected by the University of California, Los Angeles Pediatrics/Hematology/Oncology Department and is transported in an impenetrable container to the BM/HPSC lab (CHS 46-126) for further processing.

At the end of the apheresis collection, when prompted by COBE Spectra (or equivalent), seal and remove the Hematopoietic Progenitor Cells, Apheresis product, and plasma (if collected). Be sure the product has been labeled before disconnecting and that the label is complete.

Place Hematopoietic Progenitor Cells, Apheresis product in a secondary plastic bag and seal to prevent leakage. Place plasma, if collected, into a separate plastic bag and seal. Place any extra samples collected during and/or at the end of the procedure into a separate plastic bag and seal.

Registered Nurse (RN) or Clinical Laboratory Specialist (CLS) brings the product in shipping container, as well as accompanying paperwork, from collection site to the BM/HPSC lab to complete processing.

Hematopoietic Progenitor Cells, Marrow (HPC, M) is collected in the OR and transported in an impenetrable container (e.g. Room temperature cooler) to the BM/HPSC lab for further processing, or it is received in the BM/HPSC lab from the National Marrow Donor Program.

Hematopoietic Progenitor Cells, Umbilical Cord Blood (HPC, UCB) is delivered frozen to the BM/HPSC lab.

Transport of Hematopoietic Progenitor Cell Products, by CGTL personnel, from the procurement sites to the BM/HPSC lab (CHS 46-126) and from the BM/HPSC lab to the CGTL (Factor 14-246 or 14-650).

The product is assigned an identification number.

Place a room temperature gel ice pack and thermometer inside a MiniMate Ice Chest (or equivalent). The temperature must be between 20-25°C.

Take the transport container to the product collection site.

The cell product is released from the BM/HPSC Lab and placed in the plastic bag(s) and into the transport container.

Take the transport container with the product inside, and any relevant paperwork, to the final destination.

When the product arrives at the final destination, it is recorded in the log book, or equivalent (e.g. Transduction Worksheet).

Samples of the product are taken to determine sterility and cell enumeration (e.g. CD34+ cells).

Transport of HPC Product from CGTL to the Pediatric Heme/Onc Unit (3rd floor RRMC) for Infusion:

Infusion of HPC Product (viable, non-frozen):

After completion of specimen processing, the cells for infusion are put into a sterile 60cc syringe for infusion.

Label the syringe and place in a ziplock-type bag.

The bag containing the syringe is then placed into an empty ice chest to maintain room temperature during transport.

The syringe is taken to the infusion facility as soon as possible.

The Disposition of the Final Cellular Product (Form 1000A) will accompany the syringe to the infusion center.

The Disposition of the Final Cellular Product form is completely filled out by all individuals indicated.

When completed, the original document will be retained at the Clinical Gene Therapy Laboratory and filed in the study binder of the respective subject. Additional copies will be available upon request to regulatory agencies.

Transport of HPC Product from CGTL to Control Rate and Liquid Nitrogen Freezers, or for Dump Freezing

The HPC product is transported to the Control Rate Freezer at room temperature.

The product is frozen following SOP #6000 – Control Rate Freezer.

The product is removed from the Control Rate Freezer and placed in dry ice.

The product is taken to the Liquid Nitrogen Freezer in Factor 14-938 and stored.

The number of samples and their location is recorded in the Freezer Log Book.

For Dump Freezing, the cells are transported at room temperature to the -20°C freezer (14-246 Factor) and placed there overnight. The following day, they are placed in dry ice and moved to the Liquid Nitrogen Freezer.

The number of samples and their location is recorded in the Freezer Log Book.

Transport for Bedside Thawing:

A cart containing a Liquid Nitrogen Shipper and a 37°C water bath is prepared.
The frozen cells are transferred from the Liquid Nitrogen Freezer to the Liquid Nitrogen Shipper.

The cells are taken to the bedside of the patient and thawed in the 37°C water bath.
The cells are aspirated into a sterile syringe.
The cells are then given to the RN for infusion into the patient.

Calculations: Not Applicable.

Endpoint: Not Applicable.

Corrective Action: Not Applicable.

Attachments: Form 1000A

